#### 10.4.1 Concomitant Medication and Supportive Care Guidelines

##### 10.4.1.1 REQUIRED CONCOMITANT THERAPY

There is no required concomitant medication for this study.

##### 10.4.1.2 RECOMMENDED CONCOMITANT THERAPY

There is no recommended concomitant therapy for this study.

Standard of care will be delivered for patients suffering from respiratory distress or compromise due to moderate to severe COVID-19 infection per the treating physician(s) and/or institutional guidelines; in accordance with evolving CDC guidelines, local-state healthcare recommendations, availability of healthcare resources and FDA approvals and emergency use only approvals. Please refer to section 4.

##### 10.4.1.3 PROHIBITED OR RESTRICTED CONCOMITANT MEDICATIONS

Anti-cytokine based therapy (e.g. Tocilizumab or anti-IL-6 therapy)  
Convalescent plasma therapy recovered from COVID-19 patients\*  
Immunomodulatory therapy (e.g. Remicade, Sulfasalazine)  
Oncologic therapy (e.g. chemotherapy, biotherapy)  
Oncologic Immunotherapy (e.g. anti-PD-L1, anti-PD-1, anti-CTLA-4)  
Hydroxychloroquine/chloroquine will be stopped at randomization  
Anti-viral therapy (Remdesivir would not be prohibited)

\*Due to FDA EUA for COVID-19 convalescent plasma (CCP), patients receiving CCP will be eligible for this study. It is strongly preferred that participants will have received CCP prior to first dosing of ATI-450/placebo.

#### 10.4.2 VACCINES

The inactivated seasonal influenza vaccine can be given to participants while on therapy without restriction. Influenza vaccines containing live virus or other clinically indicated vaccinations for infectious diseases (i.e., pneumovax, varicella, etc.) may be permitted, but must be discussed with the Sponsor/Investigator and may require a study drug washout period prior to and after administration of the vaccine.

Patients cannot enroll in a concurrent COVID-19 vaccination clinical trial while in this 60 day study period. However, patients enrolled in a COVID-19 vaccination trial that become hospitalized with worsening hypoxic respiratory distress will be eligible for the ATI-450 clinical study provided they meet all other inclusion-exclusion criteria and will participate in both studies.

#### 10.4.3 DIET

Participants should maintain a normal diet unless modifications are required to manage adverse events such as diarrhea, nausea or vomiting, or intubation.

## 11 DOSING DELAYS/DOSE MODIFICATIONS

### 11.1 Dose Reduction Steps for ATI-450

No planned dosing reductions.

### 11.2 Dose Modification Guidelines

A patient experiencing a SAE will be evaluated for whether this is attributable to the drug or due to the patient's disease progression course in order to determine whether the patient should remain on study treatment.

Dose modifications are not permitted in this study.

### 11.3 Treatment Duration

Participants will receive treatment until there is unacceptable toxicity or the participant or treating physician determines it is not in the participant's best interest to continue.

There will be no additional medication provided to participants once the 14 day cycle has been completed.

#### 11.3.1 PARTICIPANT ACCESS TO STUDY AGENT AT STUDY CLOSURE

Participants will not have access to the study agent at study closure.

### 11.4 Participant Discontinuation/Withdrawal from the Study

- Duration of therapy will depend on individual response, evidence of disease progression and tolerance. Any one of the listed items below will be defined as a stopping criteria event. Participants will be removed from protocol therapy for any of the unacceptable adverse event listed below. Participants will have study treatment withdrawn but will remain in the study for follow-up, if any of the following occur:
  - Intubation and ventilation
  - Intercurrent illness that prevents further administration of treatment.
  - Unacceptable adverse event(s) defined as:
    - Malignancy (except for non-melanoma skin cancers)
    - Hepatitis B re-activation
    - Rhabdomyolysis
    - Demyelinating disease
    - Heart failure
    - Lupus-like syndrome

- Hypersensitivity reaction
- Gastrointestinal perforation
- WBC  $<1 \times 10^3/\mu\text{l}$
- ANC  $<0.5 \times 10^3/\mu\text{l}$
- Platelet count  $<50 \times 10^3/\mu\text{l}$
- Hemoglobin:  $<6.5 \text{ g/dl}$
- AST, ALT:
  - $>5 \times \text{ULN}$
  - $>3 \times \text{ULN}$  and (total bilirubin  $>2 \times \text{ULN}$  or international normalized ratio [INR]  $>1.5$ )
  - $>3 \times \text{ULN}$  with appearance of fatigue, nausea, vomiting, right upper quadrant pain or tenderness, fever, rash and/or eosinophilia ( $>5\%$ )
- Serum creatinine:  $>2 \times \text{ULN}$
- Serious bacterial or fungal infection
- Other major developing illness or conditions at the discretion of the treating physician
- Participant demonstrates an inability or unwillingness to comply with the oral medication regimen and/or documentation requirements
- Participant decides to withdraw from the protocol therapy
- General or specific changes in the participant's condition render the participant unacceptable for further treatment in the judgment of the treating investigator
- Major violation of the study protocol (i.e., unable to adhere to study schedule) that in the opinion of the treating investigator, puts the participant at undue risk
- Discontinuation of the study by KUMC
- Confirmed pregnancy
- Completed Overall Survival (OS) follow up as per protocol
- Lost to follow-up
- Death

Participants will be removed from the protocol therapy when any of these criteria apply. The reason for removal from protocol therapy, and the date the participant was removed, must be documented in the electronic case report form (eCRF). Alternative care options will be discussed with the participant. Safety monitoring and follow-up assessments should continue as appropriate according to the study schedule, unless the participant has withdrawn consent for study participation. Development of bacterial or fungal sepsis, agranulocytosis, hypersensitivity reaction, et al., will be followed until resolution or stabilization of the adverse event.

When a participant is removed from protocol therapy and/or is off of the study, the relevant Off-Treatment/Off-Study information will be updated in CRIS. In the event of unusual or life-threatening complications, treating investigators must immediately notify the Sponsor/Investigator.

## 12 ADVERSE EVENTS/SERIOUS ADVERSE EVENTS

Although pregnancy is not always serious by regulatory definition, for the purposes of this protocol, this event is considered to be an SAE and follow the SAE reporting timeline.

Refer to Appendix A for additional Adverse Event/Serious Adverse Event information.

### 12.1 Adverse Event Monitoring

Medical history adverse events are recorded and graded using Common Terminology Criteria for Adverse Events (CTCAE) version 5.0. Serious adverse event and adverse event monitoring begins after initiation of study treatment and continues until the Day 60 safety follow-up. This Day 60 follow-up check and will be done by phone.

### 12.2 Adverse Event Reporting

Information for adverse events, whether reported by the participant, directly observed or detected by physical examination, laboratory test or other means, will be collected, recorded, followed and reported in the CRIS system within 5 days of being reported.

All adverse events experienced by participants will be collected. Medical conditions are collected as baseline adverse events and evaluated as above. Additional adverse event monitoring begins after initiation of study treatment and continues until the 60 day safety follow up.

Participants who experience an ongoing adverse event related to a study procedure and/or study medication beyond the 60 day safety follow up will continue to be contacted by a member of the study team until the event is resolved, stabilized, or determined to be irreversible by the Sponsor/Investigator.

Study participants should also be instructed to report any new serious post-study event(s) that might reasonably be related to participation in this study.

### 12.3 Serious Adverse Event Reporting

SAEs, and follow-up information regarding SAEs, regardless of expectedness or relationship will be reported within 24 hours of notification as follows:

- Enter into CRIS (Velos) system
- Submit a complete FDA 3500A MedWatch form and all supporting documents to both KUCC Regulatory department: [[contact]](mailto:[contact])
- and
- [[contact]](mailto:[contact]) (or by fax to [contact]).

Follow-up source documentation is required within 5 days.

Local policy will be followed for reporting SAEs to the IRB.

### 12.3.1 Pregnancy Reporting

If a woman becomes pregnant or suspects that she is pregnant while participating in this study or within **30 Days** after the last dose, she must inform the investigator immediately and permanently discontinue study drug. Reporting requirements are the same as for an SAE in above. The pregnancy must be followed for the final pregnancy outcome.

If a female partner of a male participant becomes pregnant during the male participants participation, or within **90 Days** of his discontinuing treatment in this study, he must inform the investigator immediately. Reporting requirements are the same as for an SAE above. Every effort should be made to follow the pregnancy for the final pregnancy outcome.

## 12.4 IND Safety Report

The Sponsor will review all IND Safety Reports and ensure they are distributed to the participating institutions. Participating Institutions will review/submit to the IRB according to their institutional policies and procedures.

All affiliate site INDSR submissions, along with IRB acknowledgement are to be forwarded to The University of Kansas Cancer Center IIT Regulatory Department for placement within the trial master file.

Also, an email or fax reporting on SAEs should be sent to [[contact]](mailto:[contact]) (or by fax to [contact]).

## 13 MEASUREMENT OF EFFECT

Subjects will be followed daily with monitoring for hypoxic respiratory failure.

Change from baseline to time of discharge in lab values for D-dimer, hsCRP, ferritin, LDH, pro-calcitonin.

ATI-450 mediated inflammatory cytokine (IL-1b, IL6, IL-8, TNFa) reduction will be measured from baseline, during drug treatment and at the final safety follow-up visit to assess for reduction in cytokine levels.

## 14 TRANSLATIONAL AND BIOCHEMICAL SCIENCE

### 14.1.1 COLLECTION OF SAMPLES

All COVID-19 samples will be collected and processed using an Institutional Biosafety Committee (IBC) approved protocol. On the selected days per the study table, we will obtain up to 4 purple top (EDTA) tubes, 1 red top tube (serum), 1 buccal swabs scrapings, saliva- collection, and 1 urine specimen cup. At KUMC, all research blood and tissue samples obtained on the patient floor will be sent to the Centralized Clinical lab and material will be picked up on ice by University of Kansas Medical Center (KUMC) Biorepository Core Facility (BRCF)-Biobanking and Biomarker Validation (BBV) core facility. All samples

from KUMC main site will attempt to be isolated for plasma, serum, PBMC's, et al., within 1-2 hours after being taken out from the patient.

Samples originating outside of KUMC will be processed according to the provided lab protocol. Samples will be stored in screw cap vials and labelled appropriately. Samples will be snap frozen in liquid nitrogen and then stored at -80°C. Samples will be shipped to the University of Kansas Medical Center Biorepository Core Facility (BRCF)-Biobanking and Biomarker Validation (BBV) core facility and/or to contracted consulting lab(s) on dry ice and kept frozen for long term sample storage. Samples will be shipped as a Category B Biologic substance and follow standard packaging and shipping procedures as regulated by IATA. For samples originating outside of Kansas City area, these samples will be FedEx shipped overnight in batches to KUMC central repository and/or Aclaris and/or contracted laboratory.

Blood samples will be used to generate plasma, serum, PBMC, and neutrophil isolates. From the PBMCs, samples will be processed for immunophenotyping, RNA and protein isolation. The blood sample will be further processed to obtain neutrophils. Buccal mucosa specimens will be processed for DNA. Urine samples will be collected as well.

Unused tissue (e.g. plasma, buffy coat cells) will be stored at -80°C in the BRCF for future analysis up to 3 years after the study has completed. Samples in storage after this time maybe disposed of or maintained for ongoing studies.

#### 14.1.2 CYTOKINE SECONDARY ENDPOINT

At baseline (d1), d3, d7 , d14 or discharge if <d14 and d28, we will collect 1 tube of blood to isolate serum. Blood will be collected on the floors, sent to the clinical lab and transported to the KUMC Biospecimen and Biomarker Validation (BBV) Core in the Biospecimen Repository Core Facility (BRCF) within 2 hour of being drawn (within 4 hours from outside hospital). All work described is approved by the University of Kansas IBC.

Samples will be batch assayed in order to minimize variations between patients sampled on different days. Cytokines to be assayed will include: IL-1 $\beta$ , IL-6, IL-8, TNF $\alpha$ .

**Luminex or MSD Assays** - Circulating levels of cytokines of interest in serum or plasma will be quantified using multiplexed fluorescent magnetic bead-based immunoassays (Millipore-Sigma) following manufacturer's protocols. Briefly, an overnight bead capture will be performed at 4 °C in black-walled 96-well plates on a plate shaker at the specified dilution of the serum/plasma. Detection and reporter antibodies (streptavidin-conjugated phycoerythrin) will be added on day 2 and incubated at room temperature with shaking. A Bioplex 200 instrument (BioRad) will be used to measure the mean fluorescent intensity (MFI) values for each marker for each test sample and known standards. Standard curves generated using MFI versus concentration data will be used to calculate the cytokine levels in each sample.

### 14.1.3 EXPLORATORY ENDPOINTS

#### 14.1.3.1 ADDITIONAL INFLAMMATORY CYTOKINE

Blood collected for serum cytokine analysis as described in 14.1.1 will be utilized for inflammatory cytokine analysis using the same Luminex platform operated by the BBV core facility. Additional inflammatory cytokines to be analyzed include: GM-CSF, sIL-2R, IFN $\gamma$ , IL-17, IL-18, IL-10, IL-1 $\alpha$ , IL-1RA, G-CSF, MIP1 $\alpha$ , and MCP1, IP10, TGF- $\beta$ 1.

#### 14.1.3.2 IMMUNE PHENOTYPING AND CELL WORK

At baseline (d1), d7, d14 or discharge if <d14 and d28, we will collect 3 tubes of whole blood which will be separated into buffy coat-PBMCs and plasma for immune cell phenotyping analysis. The banked plasma will be used for future exosome analysis, cfDNA analysis or ex-vivo stimulation assays. A 4th tube of blood will be processed by the [name] lab using a rapid separation technique using Histopaq 1077 which allows for PBMC isolation in under 2 minutes. Transcriptomic analysis, RNA and immunoblot analysis of p38-MK2-HSP27 signaling axis will be analyzed using this technique. Blood will be collected and processed uniformly by the BBV for buffy coat-PBMCs within 2 hour of being drawn. In 10 ml of blood, approximately 10 million PBMC's can be harvested from the buffy coat but the true number will vary based on numerous health factors with this patient population. Total cells numbers will be counted using an automated cell counter with a disposable hemocytometer. Test for Immunophenotyping will follow standard established FACS analysis protocol; RNA and immunoblot will follow standard qRT-PCR and Western blot techniques using previously published methods.

#### 14.1.3.3 NANOSTRING OR EQUIVALENT TRANSCRIPTOMIC ANALYSIS

PBMC's that are rapidly isolated, and neutrophils slated for RNA analysis via Nanostring or equivalent procedure will be lysed in RLT buffer (Qiagen) and stored at -80°C until ready for RNA processing. We will utilize 300 ng of RNA for targeted transcriptomic analysis comparing the placebo to the drug treatment groups at baseline and at day 7. Alternative large-scale transcriptomic analysis procedures will be considered based on cost and efficiency.

#### 14.1.3.4 NEUTROPHIL ISOLATION AND NEUTROPHIL EXTRACELLULAR TRAP

One tube of blood will be used to isolate PBMC's and the pelleted erythrocytes-neutrophils will be further processed to yield neutrophils. These neutrophils will undergo further ex-vivo analysis to examine amount of neutrophil extracellular trap formation in the presence or absence of MK2 inhibition. Additional RNA and protein work will be performed on these cells.

#### 14.1.3.5 BUCCAL MUCOSA SAMPLE COLLECTION

Buccal mucosa swab will be taken at baseline and at day 7 and day 28.

The buccal mucosa swab will be performed by the patient, or study personnel (if patient is unable or would prefer), to collect epithelial cell lining and bacteria within the patient's cheeks and gingival gum area. They

will place the swab/cytobrush in the viral transport medium containing vial. This medium will inactivate virus and cells immediately. Tissue will be harvested for future DNA analysis and will temporarily be stored.

#### 14.1.3.6 SALIVA SAMPLE COLLECTION

We will collect saliva into containers at baseline, day 14 (or at discharge less than day 14) and day 28. Collection tubes will be sealed and the external surface of the collection tubes will be wiped down with disinfecting wipes and temporarily stored.

#### 14.1.3.7 URINE SAMPLES

Urine samples will be collected at the pre-specified time points. Samples will be aliquoted into 1 ml volume into a 1.5 ml cryovial tube, frozen and then stored at -80°C freezer in the BRCF. Future analysis will examine urine markers for fibrosis and inflammation.

### 15 STATISTICAL CONSIDERATIONS

Details of the statistical summaries will be provided in the study-specific statistical analysis plan (SAP). Generally, the objectives for this study will be assessed via point estimates and corresponding confidence intervals.

#### 15.1 Sample Size Justification

Data from 36 patients (18 randomized to ATI-450 and 18 to Placebo) provide enough precision to ensure that the expected asymmetric 70% confidence interval for the difference in the proportion of responders will be no wider than 31 percentage points. This level of precision for the planned 70% confidence interval will facilitate development decisions in accordance with the methods of Frewer et al. The estimate of the expected 70% confidence interval assumed that the placebo response rate would be approximately 50% on Day 14. The 50% response rate assumption was obtained from the proportion of patients that were either not hospitalized or hospitalized but not requiring supplemental oxygen on Day 14 from the study of lopinavir-ritonavir in adults with severe COVID-19 (Cao B., et al. NEJM 2020).

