## PROTOCOL SUMMARY

Title	A double-blind, randomized controlled trial of ATI-450 in patients with moderate-severe COVID-19
Protocol Number	IIT-2020-ATI-450-COVID-19
Phase	2a
Design	Phase 2a, randomized, double-blind, placebo controlled, parallel group study in patients with moderate to severe COVID-19
Study Duration	9 months
Study Center(s)	The University of Kansas Medical Center
Objectives	
Primary Objective To assess the efficacy of ATI-450 on hypoxic respiratory failure-free survival in patients with moderate-severe COVID-19
 
Secondary Objectives To assess the clinical efficacy of ATI-450 on respiratory function and survival in patients with moderate-severe COVID-19
 
To assess the anti-inflammatory and immune effect of ATI-450
 
To assess the safety of ATI-450 in patients with moderate-severe COVID-19
 
Exploratory Objective To assess the pharmacodynamics of ATI-450 in patients with moderate-severe COVID-19

Number of Participants	20
Diagnosis and Main Inclusion Criteria	
Has laboratory-confirmed COVID-19 coronavirus infection as determined by polymerase chain reaction (PCR), or other commercial or public health assay in nasopharyngeal testing within 14 days of enrollment AND,
 
Hospitalized as a result of symptoms and signs related to COVID-19 infection, and ≤14 days since positive test AND:
 
Evidence of hypoxic respiratory failure: SpO2 ≤93% on room air or supplemental oxygen, or SpO2 ≥93% requiring ≥ 2L O2, or PaO2/FiO2 ratio <300mmHg, or tachypnea (respiratory rate ≥ 30 breaths/min) and
 
Evidence of pulmonary involvement by chest imaging or pulmonary exam

Study Product(s), Dose, Route, Regimen	
Dose of ATI-450
 
50 mg (as determined from Phase I study) per dose. (100 mg per day).
 
or
 
Placebo

	
Route Oral tablet
 
Schedule Pill will be taken twice daily preferably spaced 12 ±1 hours apart.

Duration of Administration	Up to a maximum of 14 days while inpatient. Patients discharged home or new requirement for mechanical ventilation will be discontinued off drug permanently.
Interim Monitoring	The study will be monitored at appropriate intervals, no less than those assigned per risk level designation, to assure compliance to GCP and to assess the data quality and study integrity.

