Statistical Methodology	
Details of the statistical analyses and summaries will be provided in the study-specific statistical analysis plan (SAP).
 
Determination of Sample Size Data from 36 patients (18 randomized to ATI-450 and 18 to Placebo) provide enough precision to ensure that the expected asymmetric 70% confidence interval for the difference in the proportion of responders will be no wider than 31 percentage points. This level of precision for the planned 70% confidence interval will facilitate development decisions in accordance with the methods of Frewer et al.
 
Analysis Populations
 
 
• The Full Analysis Set (FAS) will include all patients who have been administered at least one dose of study medication.
 
• The Per-Protocol population will include all FAS patients who have completed their Day 14 visit, and have continued study drug administration through Day 14, or were discharged with a successful outcome prior to day 14.
 
 
Efficacy Analyses and Summaries
 
Primary Efficacy Analysis The primary assessment of efficacy for this study will be the point estimate and corresponding asymmetric 70% confidence interval for the difference in proportions of responders between the ATI-450 and Placebo groups. All subjects who are alive, free of respiratory failure (do not require supplemental oxygen) and do not experience negative intercurrent events by Day 14 of the trial will be considered responders. The point estimate and corresponding 70% confidence interval will be derived using a logistic regression model that includes treatment group, baseline age group (<60 versus ≥60), and gender as factors.
 
Secondary Efficacy Analyses Supportive analyses will be conducted on the secondary efficacy endpoints described in Section 3.5. Categorical variables will be analyzed using a logistic regression similar to that described for the primary

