### 15.3 Description of Statistical Methods

#### **Efficacy Analyses**

##### **Primary Efficacy Analysis**

The study is hypothesis generating. The primary assessment of efficacy for this study will be the point estimate and corresponding asymmetric 70% confidence interval for the difference in proportions of responders between the ATI-450 and Placebo groups. All subjects who are alive, free of respiratory failure (do not require supplemental oxygen) by Day 14 of the trial will be considered responders. The point estimate and corresponding 70% confidence interval will be derived using a logistic regression model that includes treatment group, baseline age group (<60 versus  $\geq 60$ ), and gender as factors.

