A Trial of Aclaris Therapeutics, Inc. (ATI)-450 in Patients With Moderate-severe Novel Coronavirus Disease 2019 (COVID-19)

Document Date: 3/27/23

Trial Number: NCT04481685

Statistical Analysis Plan

Study Title: A double-blind, randomized, controlled trial of ATI-450 in

patients with moderate-severe COVID-19

Phase: 2A

Protocol No.: IIT-2020-ATI-450-COVID-19

This document describes the statistical methods and data presentations to be used in the summary and analysis of data from Protocol IIT-2020-ATI-450-COVID-19 by the Department of Biostatistics and Data Science of the University of Kansas Medical Center based on the criterion for investigator-initiated trials (IITs) of KUMC.

Study Overview

IIT-2020-ATI-450-COVID-19 is a Phase 2A, double-blinded, randomized, placebo-controlled, proof of concept, safety, efficacy, multi-center study of ATI-450 as monotherapy for treating patients with moderate to severe COVID-19 disease.

Patients who have laboratory-confirmed COVID-19 as determined by polymerase chain reaction (PCR), or other commercial or public health assay in oropharyngeal or nasopharyngeal testing within 14 days of hospitalization, and are currently hospitalized as a result of symptoms and signs related to COVID-19 pneumonia with evidence of hypoxic respiratory failure: pulse oximeter measurement of oxygen saturation (SpO_2) $\leq 93\%$, or $\text{SpO}_2 > 93\%$ requiring $\geq 2\text{L}$ of supplement oxygen (O_2), or partial pressure of oxygen (PaO_2)/ fraction of inspired oxygen (FiO_2) ratio $< 300\text{mmHg}$, or tachypnea (respiratory rate > 30 breaths/min) or evidence of pulmonary involvement by chest imaging or pulmonary exam will be eligible for enrollment into the study. Eligible patients will be randomized in a 1:1 ratio to either 50 mg oral ATI-450 twice daily (BID) or placebo BID for 14 days or until patient discharge whichever is earlier.

Treatment Assignment:

A total of approximately 20 patients will be randomized in a 1:1 ratio:

- Placebo oral tablet BID for 14 days
- ATI-450 oral tablet, 50 mg, BID for 14 days

Survival follow up assessments will be conducted 28-, 45- and 60-Days post hospital Day-1 and all participants should complete these visits. Exceptions include death, lost to follow-up or the participant withdrawing consent for follow-up all of which should be documented in the participants medical record and EDC.

Study objectives

Primary Objective:

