Sample Size Justification

Data from 20 patients (10 randomized to ATI-450 and 10 to Placebo) provide some preliminary information about the efficacy and safety of ATI-450. No hypothesis will be formally tested. The mean and exact 90% confidence intervals for within-group event rates will be estimated and no between group difference will be estimated.

Randomization and Blinding

Prior to the start of the study, the University of Kansas Medical Center will generate a list of randomization numbers that shall be transmitted to the assigned clinical packaging organization for study medication labeling. The randomization list will be stored with access limited to designated personnel for study medication labeling. The randomization list will be made available, as appropriate, to unblind the database.

In the treatment period, subjects will be assigned to 1 of the 2 treatment groups in a random manner and at a 1:1 ratio stratified by baseline age group (<60 versus \geq 60). At the Day 1 visit an investigational center staff member will assign study medication to eligible subjects by selecting an appropriate Subject Kit. The staff member must select Subject Kits in chronological sequence and in an ascending numerical order starting with the lowest available Subject Kit number. No Subject Kit number may be omitted or reused. The Subject Kit number is the randomization number.

This study uses a double-blind design. The study medications are indistinguishable in appearance, as packaged and labeled.

Analysis populations

- The Full Analysis Set (FAS) will include all patients who have been administered at least one dose of study medication. The FAS will be population used in the primary efficacy analysis. The FAS will also be the population used secondary efficacy analyses and summaries as well as the population used in all safety summaries. The FAS will be analyzed/summarized as randomized when applied to efficacy endpoints. The FAS will be analyzed/summarized as treated when applied to safety endpoints.
- The Per-Protocol population will include all FAS patients who have completed their Day 14 visit and have continued study drug administration through Day 14 or were successfully discharged prior to Day 14. The Per-protocol population will be used for the primary efficacy analysis. Summaries and analyses using the per-protocol population will be done as treated.

Statistical Analysis Methods

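### The protocol justifies 36 patients by a 70% CI no wider than 31 points, but its own Summary and the SAP set the size at 20. At 10 per arm the width is about 41-48 points (both arms 50%), and the SAP's primary analysis drops that interval.

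*Protocol*

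**What the plan says.** **Sample size.** The protocol gives two figures. In the Protocol Summary the row "Number of Participants" gives 20. The Statistical Methodology row of the same table says "Data from 36 patients (18 randomized to ATI-450 and 18 to Placebo) provide enough precision", and Section 15.1 repeats this. The SAP agrees with 20. Under Treatment Assignment it says "A total of approximately 20 patients will be randomized in a 1:1 ratio", and its sample-size section reads "Data from 20 patients (10 randomized to ATI-450 and 10 to Placebo) provide some preliminary information about the efficacy and safety of ATI-450".

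**Precision.** Section 15.1 rests the 36 on one statement, that the "expected asymmetric 70% confidence interval for the difference in the proportion of responders will be no wider than 31 percentage points". It adds: "This level of precision for the planned 70% confidence interval will facilitate development decisions". The only response rate given is about 50% on placebo at Day 14. The SAP's justification for 20 patients states no interval width.

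**Primary interval.** Protocol Section 15.3 makes primary the point estimate and "corresponding asymmetric 70% confidence interval for the difference in proportions of responders between the ATI-450 and Placebo groups", from a logistic model with treatment, age group and gender. The SAP's primary analysis is an exact 90% (Clopper-Pearson) interval for the responder proportion in each arm. Its sample-size section says that "no between group difference will be estimated".

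**The concern.** This is an estimation study with no formal test, so expected precision is the whole case for its size. In the protocol that case belongs to 36 patients, while the enrolment figure in the Summary and the SAP is 20. Anyone reading the protocol alone would expect an interval that 20 patients cannot deliver, and would read that the interval supports development decisions. Under the SAP, the primary analysis does not compute that interval at all. The two current documents therefore give different answers on the number of patients and on the primary quantity, confidence level and method.

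**Working it through.** **Inputs.** From the protocol: 18 per arm, 50% placebo response, 70% confidence, 31 points (Section 15.1). From the SAP: 10 per arm. Not stated, so assumed and varied: the ATI-450 rate (50% to 90%), the tail split of the asymmetric interval (15/15, 20/10, 25/5), and the interval method. Covariate adjustment is ignored because no covariate inputs are given.

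**Formula.** Plug-in Wald width = (z_lower + z_upper) × √[(p₁q₁ + p₂q₂)/n]. The z sums are 2 × 1.036 = 2.073 (15/15), 0.842 + 1.282 = 2.123 (20/10) and 2.319 (25/5). Expected widths for Wald, Newcombe and Agresti-Caffo come from full binomial enumeration.

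**Step 1: the protocol's own figure, 18 per arm.** With both arms at 50%, √(0.5/18) = 0.1667, so the Wald width is 2.073 × 0.1667 = 34.5 points (15/15) or 2.123 × 0.1667 = 35.4 points (20/10). To get 31 points with 15/15 tails, p₁q₁ = (0.31/2.073)² × 18 − 0.25 = 0.153, which is an ATI-450 rate of about 81%. With 20/10 tails it is about 84%. Across the methods, 31 points needs an ATI-450 rate of 70-81% (15/15), 73-84% (20/10) or 80-92% (25/5). The figure is attainable, but it cannot be reproduced from the text because neither the ATI-450 rate nor the tail split is given.

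**Step 2: 10 per arm, both arms 50%.** √(0.5/10) = 0.2236, so the Wald width is 46.4 points (15/15) or 47.5 points (20/10).

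| Width in points, both arms 50% | 18/arm, 15/15 | 18/arm, 20/10 | 10/arm, 15/15 | 10/arm, 20/10 |
|---|---|---|---|---|
| Wald, plug-in | 34.5 | 35.4 | 46.4 | 47.5 |
| Miettinen-Nurminen | 34.5 | 35.3 | 46.3 | 47.2 |
| Newcombe, plug-in | 33.6 | 34.2 | 44.0 | 44.7 |
| Wald, expected | 33.6 | 34.4 | 43.9 | 45.0 |
| Newcombe, expected | 32.7 | 33.3 | 42.1 | 42.8 |
| Agresti-Caffo, expected | 32.0 | 32.8 | 40.8 | 41.8 |

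With 25/5 tails the ranges are 35.8-38.7 points (18 per arm) and 45.5-51.9 points (10 per arm). A continuity-corrected Wald interval (15/15) is much wider: 45.7 and 66.4 points.

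**Step 3: sensitivity to the ATI-450 rate, 10 per arm.** At 80% on ATI-450 the widths (15/15 and 20/10) are 38.2-43.0 points, against 29.6-32.0 at 18 per arm. At 90% they are 35.3-39.1 points. The smallest value over 50% to 90% is 35.3 points (expected Newcombe, 20/10, 90%). As a check free of these assumptions, scaling the stated figure gives 31 × √(18/10) = 41.6 points.

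**Step 4: what the SAP's interval gives.** The exact 90% interval for 5 of 10 responders runs from 22.2% to 77.8%, about 56 points, which is the widest case. The expected width is 53 points at a true rate of 50%, 49.5 at 70% and 37 at 90%.

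**The case against.** The strongest reply is that the SAP already settles the matter. The protocol leaves analysis details to it, and it has its own modest justification for 20 patients and uses different intervals. No text attaches 31 points to 20 patients. On this view the fault is protocol wording that was not updated, in a study described as hypothesis generating. That is right about the consequence: no error rate changes and no patients need adding. It does not remove the conflict. The protocol disagrees with itself on 20 versus 36, the SAP does not say that it replaces Sections 15.1 or 15.3, and a change of primary quantity, level and method is more than a detail.

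A second reply is that 31 against 41-48 is not like for like, since at 50% in both arms 18 per arm already gives 32-35. This is fair. The matched comparisons are 32-35 against 41-48, or 31 against about 42. Either way the precision is lost.

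Third, the planned interval is covariate-adjusted, and none of these calculations adjust. That limits the exact widths, which hold for unadjusted methods only. Finally, whether the wider interval would defeat the intended decisions depends on a cited method that is not in the documents, so nothing is claimed on that.

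**Conclusion.** The concern holds. The 31-point precision belongs to 36 patients and is not available at 20. With placebo at 50%, ATI-450 assumed at 50%, 15/15 or 20/10 tails and no covariate adjustment, the width at 10 per arm is about 41-48 points. It stays at 35 points or more for ATI-450 rates up to 90%, with 25/5 tails as well. At 36 patients the 31 is possible but unverifiable, because it needs an unstated ATI-450 rate of about 70-84% (15/15 or 20/10). Separately, the protocol and the SAP name different primary intervals, and the SAP's does not estimate the difference on which the protocol's sample size was based. This needs correcting because sample size and primary analysis are core design statements.

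**What to change.** 1. Use one sample size, 20 (10 per arm), in both rows of the Protocol Summary and in Section 15.1.
2. Delete the 31-point statement. Alternatively, restate it for 10 per arm as about 41-48 points, giving the assumed ATI-450 rate (50%), the tail split (15/15 or 20/10) and the method. Deletion is cleaner if the within-arm intervals are kept as primary.
3. Remove or requalify the sentence linking that precision to development decisions.
4. Name the same primary interval in the Protocol Summary, Section 15.3 and the SAP. The SAP's Secondary Efficacy Analyses still mention an interval for a difference in proportions for binary endpoints, so align that with its statement that no difference will be estimated.
5. In the SAP's sample-size section, add only the within-arm width, for example 22% to 78% (about 56 points) at 5 of 10. The 70% difference width does not belong there.

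The cost is wording in the Summary, Sections 15.1 and 15.3 and the SAP, and a less favourable precision statement. No extra patients are asked for.
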